#### *Duration from reversal to extubation*

Summary statistics (mean  $\pm$  standard deviation, median, IQR) will be summarized for each treatment condition. Two-sided t-test for independent groups will be used to compare the above variables between the two groups. P-values will be reported and 95% confidence interval of group difference will also be reported. Wilcoxon rank sum test will be used instead in the rare event of non-normality.

#### *Surgical rating scores*

Summary statistics (mean  $\pm$  standard deviation, median, IQR) will be computed for surgical rating scores for each patient, per each treatment group. Wilcoxon sign rank tests will be used to compare surgical rating score between the two groups. P-values will be reported and 95% confidence interval of group difference will also be reported.

*Numerical pain rating, occurrence of nausea or vomiting, and level of sedation or alertness*  
Numerical pain rating score and level of alertness will be presented as a graphical display of treatment group mean or median over each of the four time points in the recovery room. Contingency table (condition\*group\*time) for nausea/vomiting will be presented. GEE (Generalized estimating equation) will be used to compare the recovery room variables between the two treatment conditions with time and treatment group as covariates. Exchangeable correlation structure will be applied. The distribution of binary variable (occurrence of nausea or vomiting) is assumed to binomial, and the distribution of other ordinal variables are assumed to poisson or negative-binomial based on the nature of data.

#### **Power analysis**

We will assume a normal distribution. Using the values found in the Casanova article, we expect the difference in moderate versus deep block peak airway pressures to be approximately 2 cmH2O, with a standard deviation of 5. Converting these numbers to mmHg, we expect to see a difference of 1.48 mmHg, and a standard deviation of 3.68 mmHg. Using an  $\alpha=0.05$ , we will need around 52 patients for a paired t-test to have approximately 81% power to detect a difference between moderate and deep peak airway pressures. We plan to enroll approximately 120 patients to account for drop outs.

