## **Methods**

This will be a single-center, prospective, randomized, two-period crossover controlled trial. Approval from the local IRB will sought and patients will provide written informed consent.

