### **Inclusion and exclusion criteria**

Inclusion criteria:

The participant must fulfill ALL the criteria listed below for entry.

- Each participant must be willing and able to provide written informed consent for the study.
- Each participant must be greater than or equal to 18 years of age.
- Each participant must be ASA class I, II or III.
- Each participant must be scheduled for elective laparoscopic surgery (this includes robotic laparoscopic s).
- Expected surgical duration of 60 min or longer

Exclusion criteria:

- Inability to give informed oral or written consent
- Known or suspected neuromuscular disorders impairing neuromuscular function;
- True allergies as defined as hypotension, bronchospasm, or anaphylaxis to muscle relaxants, anesthetics or opioids
- A history (patient or family) of malignant hyperthermia
- A contraindication for neostigmine administration
- Renal insufficiency, as defined by serum creatinine levels at 2.5 fold the normal level
- Body mass index >45 kg/m
- Significant respiratory disease.
- Planned postoperative mechanical ventilation

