## Investigational plan and treatments (see Figure 1)

Subjects will be randomly assigned to one of two study groups using a random number generator and sealed envelope technique:

Group 1 D→M: After induction and intubation, the patient will be maintained in a “deep” (post-tetanic count of zero to two) neuromuscular block (NMB). Deep NMB will be obtained with an intubating dose of rocuronium of 0.5 mg/kg or as per clinical team’s discretion. After surgical incision is made, the abdomen is insufflated, trocars are inserted, and prior to the beginning of the actual laparoscopic procedure, collection of data for “deep” NMB period will begin. Neuromuscular blockade level will be maintained and adjusted throughout the course of surgery using intravenous bolus doses of rocuronium. Dosing of rocuronium will be determined by the clinical team. Only the clinical team will administer any medications or fluids to patients enrolled in the study (no research team members will be administering drug or fluid). The surgeon will inform the study team member of the first Surgical Rating Scale (SRS) score for his/her view, and simultaneously, the first peak airway pressure and related variables will be collected (T0). For the next 20 minutes of surgery during which a “deep” NMB is being maintained, peak airway pressure, heart rate, and blood pressure will be collected every minute by the study team member (as per the anesthesia machine’s readings), and the surgeon will provide the SRS score every 5 minutes. To minimize any type of carry-over effects, after the completion of the deep NMB 20 minute period, a “transition period” will begin (T1).

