### **Statistical Analysis**

*Airway Pressure, Intra-abdominal pressure, Respiratory rate, arterial oxygen saturation, blood pressure, heart rate*

In order to obtain the most accurate measurements possible, multiple readings for the primary outcome (peak airway pressure) and secondary outcomes (respiratory rate, arterial oxygen saturation, blood pressure, and heart rate) will be collected once per minute for a maximum of 20 minutes per treatment period. Summary measures (i.e. descriptive statistics including mean  $\pm$  standard deviation, median, and interquartile range) for each data element will be generated for each patient, per each treatment period. Depending on the distribution of the peak airway pressure variable (as tested by Shapiro-Wilk tests), either a paired t-test or Wilcoxon Sign Rank test will be used to compare peak airway pressure between the two treatment conditions. Secondary outcomes

(respiratory rate, arterial oxygen saturation, blood pressure, and heartrate) will also be examined in a similar way for differences between the two treatment groups. P-values will be reported at the 95% confidence level.

Additionally, linear mixed effects models will be used for the peak airway pressure outcome, with treatment group and time as fixed effects, and subject as random effect. Group effect size and p-value will be reported at the 95% confidence level.

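### Does enrolling about 120 patients, when the power calculation asks for about 52, show that the sample size or the stated power is wrong?

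*Combined protocol and SAP*

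**What the plan says.** The Methods section of the combined protocol and SAP sets the design: "This will be a single-center, prospective, randomized, two-period crossover controlled trial". Each patient is therefore observed under both depths of block, and the number of patients equals the number of pairs. The Statistical Analysis section says that "either a paired t-test or Wilcoxon Sign Rank test will be used to compare peak airway pressure between the two treatment conditions", applied to a summary of the readings for each patient and period. It adds a linear mixed model with subject as a random effect.

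The Power analysis section starts from a difference of about 2 cmH2O "with a standard deviation of 5", taken from a published study, and converts the units: "we expect to see a difference of 1.48 mmHg, and a standard deviation of 3.68 mmHg". It concludes that "we will need around 52 patients for a paired t-test to have approximately 81% power" and continues: "We plan to enroll approximately 120 patients to account for drop outs". Drop-out is the only reason given for the larger number. The document gives no expected loss rate, no definition of an evaluable patient and no power for 120.

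**The concern.** Enrolment is 120/52 = 2.31 times the calculated need, and words such as 'around' and 'approximately' cannot absorb a gap of that size. If drop-out really is the reason, more than half of those enrolled are expected to contribute nothing to the primary comparison. That would raise doubts about selection and about whether loss differs between the two sequences. If loss is ordinary, 81% is not the power the trial will have, and some 45 to 62 patients are enrolled beyond its own calculation.

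Two features make the worry more plausible. Eligibility requires "Expected surgical duration of 60 min or longer", while the two observation windows alone take 40 minutes, and a transition is placed between them: "To minimize any type of carry-over effects, after the completion of the deep NMB 20 minute period" is how that step is introduced for the first sequence. In addition, the plan does not say whether its standard deviation is that of within-patient differences, which is the one a paired test needs.

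**Working it through.** **Inputs.** From Power analysis: α = 0.05, difference 1.48 mmHg, SD 3.68 mmHg (2 and 5 in cmH2O), 52 patients needed, about 120 enrolled. From Methods and Statistical Analysis: two-period crossover, paired test. Assumed: a two-sided test (not stated for the primary outcome), and 3.68 as the SD of within-patient differences.

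**1. The plan's own figure.** Power comes from the noncentral t distribution with n − 1 degrees of freedom and noncentrality (difference/SD)·√n.
- 1.48/3.68 = 0.402. At n = 52 the noncentrality is 0.402 × √52 = 2.90, and power is 81.2%.
- In cmH2O, 2/5 = 0.400 gives 80.8% at n = 52.
- A one-sided test would give 88.8%, so the two-sided reading is the one that matches.

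The stated figure is correct.

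**2. Loss implied by 120.** 1 − 52/120 = 0.567. Enrolment needed for 52 evaluable patients is 52/(1 − d), where d is the loss.

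| Loss d | Enrolment for 52 evaluable | Evaluable from 120 | Power from 120 |
|---|---|---|---|
| 0% | 52 | 120 | 99.2% |
| 10% | 58 | 108 | 98.5% |
| 20% | 65 | 96 | 97.4% |
| 30% | 75 | 84 | 95.4% |
| 40% | 87 | 72 | 92.0% |
| 50% | 104 | 60 | 86.5% |
| 57% | about 120 | 52 | 81.2% |

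Power does not fall below the stated level until loss passes about 57%. The excess over need is 120 − 58 = 62 patients at 10% loss and 120 − 75 = 45 at 30%.

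**3. Could 52 be per group?** Then 104 in total and 1 − 104/120 = 13.3% loss, an ordinary allowance. But 104 pairs give 98.2% power, so this reading does not produce 81%, and the crossover design rules it out.

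**4. Sensitivity to the meaning of the SD.** If 5 cmH2O is the SD within one condition, the SD of differences is 5·√(2(1 − ρ)), where ρ is the within-patient correlation. The documents give no ρ, so a range is shown.

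| ρ | SD of differences (cmH2O) | Power at 52 | Needed for 81% | Power at 120 |
|---|---|---|---|---|
| 0 | 7.07 | 51.6% | 103 | 86.7% |
| 0.3 | 5.92 | 66.7% | 73 | 95.7% |
| 0.5 | 5.00 | 80.8% | 53 | 99.1% |
| 0.7 | 3.87 | 95.5% | 33 | >99.9% |

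In the worst row, 120 leaves room for 1 − 103/120 = 14.2% loss.

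**5. The 60-minute criterion.** In a case lasting exactly 60 minutes, 60 − 40 = 20 minutes remain for access, transition and closure. Assuming 5 to 15 minutes for access and 5 to 10 for closure, the transition gets between 20 − 5 − 5 = 10 and 20 − 15 − 10 = −5 minutes. This applies only at the minimum duration and rests on assumed times. Statistical Analysis treats 20 minutes as the upper limit of readings in a period and reduces them to a summary, so a shortened second window still yields a pair.

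**The case for a change.** The best argument for a change is that a sample-size section should let the reader get from the calculation to the enrolment target, and this one does not. The one reason given leads to a 57% loss that nobody would assume without comment. A reader cannot tell whether the sponsor expects heavy loss, wants more power, or doubts the standard deviation. That criticism stands as a remark on reporting.

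The remedies that might follow from it do not stand as required changes.
- **Cutting enrolment to 52/(1 − d).** This needs a loss rate that the documents do not supply, and it removes the protection shown in step 4. It trades fewer patients for more risk and corrects no error.
- **Raising the minimum operating time.** No loss figure supports this. Loss that is heavier in the deep-to-moderate sequence is conceivable, because the block must lighten. The Surgical rating section, however, also allows a moderate block to be deepened when conditions are poor, which could disrupt the other sequence. The net direction is unknown. The plan also does not say when in a patient's course the envelope is opened, so some of the 120 may never be randomised.
- **Checking the SD on pooled data.** This adds an interim procedure. Pooling period differences across sequences would also inflate the estimate on the plan's inputs to √(3.68² + 1.48²) = 3.97, which raises the sample size by (3.97/3.68)² − 1, about 16%.

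The excess of 45 to 62 patients at 30% to 10% loss is real on the plan's own inputs. The larger number does have a use, although the plan does not claim it. Time from reversal to extubation is compared between independent groups, and with equal allocation these would hold about 60 patients each instead of 26.

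**Conclusion.** No change follows. The calculation of 52 patients for 81% power is right (81.2%). The enrolment of 120 is an unexplained margin. The two numbers do not contradict each other, because 81% is stated for 52 patients only. If 3.68 mmHg is the SD of within-patient differences and the test is two-sided, the trial has at least its stated power at any loss up to about 57%, with 97.4% at 20% loss and 95.4% at 30%. If 5 cmH2O is a per-condition SD, 120 patients still give 86.7% with zero correlation and no loss, and stay above 81% with up to about 14% loss.

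The loss rate, the definition of evaluable, the meaning of the SD and the power at 120 are details that could have been stated. Leaving them out does not affect the validity of the paired comparison, and the report can give the number analysed and the confidence interval. The suggestions that the 60-minute criterion causes heavy loss, or that loss depends on sequence, rest on assumed times and conjecture, and the conclusion does not depend on them.

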## Appendix

Table 1 Surgical rating score

1	Extremely poor conditions
2	Poor conditions
3	Acceptable conditions
4	Good conditions
5	Optimal conditions

Table 2. Observer's Assessment of Alertness and Sedation scale

Responsiveness score	Level*
Responds readily to name spoken in normal tone	0 (Alert)
Lethargic response to name spoken in normal tone	1
Responds only after name is called loudly and/or repeatedly	2
Responds only after mild prodding or shaking	3
Does not respond to mild prodding or shaking	4
Does not respond to noxious stimulus	5

